5.5.5. Time to Response

Time to response for subjects with either CR (including CR_b and CR_u) or PR as assessed by IRC is defined as the interval between the date of randomization and the date of initial documentation

of a response. Descriptive summary for time to response will be provided for each treatment group

Duration of Response

Duration of response for subjects achieving either CR (including CR_b and CR_u) or PR is defined as the interval between date of initial documentation of a response to the date of first documented evidence of progressive disease (PD) or death as assessed by IRC. The distribution for duration of response and median survival time with its 90% confidence interval will be estimated using the Kaplan-Meier product-limit method.

5.5.6. Subjects Who Proceed to Stem Cell Transplantation

The rate of subjects who proceed to stem cell transplantation will be estimated according to a proportion summarized by treatment arm. The rate will be compared between treatment arms using a 2-sided chi-square test at the 10% level of significance and 90% confidence intervals. Logistic regression analysis will also be performed to estimate an odds ratio and the associated 90% CI between the 2 treatment groups.

5.5.7. Other Efficacy Endpoints

Exploratory efficacy endpoints are as follows:

- Non-stratified Cox proportional hazards model using covariates to analyze the effect on EFS and survival will be performed, as appropriate.
- Non-stratified log-rank test for the effect of subsequent antilymphoma therapy or a conditioning regimen for stem cell transplantation on overall survival, will be performed as appropriate.
- The number (%) of subjects with subsequent antilymphoma therapy or a conditioning regimen for stem cell transplantation will be summarized by therapy type. A listing of subjects with subsequent therapy will also be provided.

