8.4. Subsequent Antilymphoma Therapies

Administration of subsequent antilymphoma therapy is not allowed until:

- Confirmed residual disease after completion of at least 3 cycles of study treatment, or
- PD (or relapse after CR) any time during treatment as established according to the criteria described in Section [9.2.5.2](#), Response Categories.

Note that the medical monitor must be notified of the subject's suspected PD and all imaging, bone marrow, and cerebrospinal fluid (CSF) disease analyses are required to be centrally reviewed before a subject is removed from study therapy. Subjects who have not progressed while on therapy and who receive subsequent therapy for NHL will continue to be followed until PD. For any subsequent antilymphoma therapy, the start date, end date, and best response should be documented in the appropriate section of the electronic CRF.

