study treatment until PD is confirmed by the central IRC. If PD is diagnosed, then the subject will discontinue study treatment, complete the End-of-Treatment visit within 30 days after the last dose of the last study treatment, and enter the Posttreatment Phase. Imaging evaluations performed on Cycle 1 Day 14 are exploratory; therefore, if PD is indicated based on these scans, investigator discretion should be used to determine if the clinical evaluation is consistent with PD. If not, the subject may continue with study treatment until confirmation of PD or the subject meets other criteria for withdrawal. If CR is confirmed at the end of 2 cycles of treatment, then the subject is eligible to proceed to stem cell transplantation.

End-of-Treatment Visit

Subjects who discontinue the last study treatment due to progression, adverse event, or other reasons and enter the Posttreatment Phase should have the End-of-Treatment visit completed before starting any subsequent antilymphoma therapy. If a subject is unable to return to the site for the End-of-Treatment visit, the subject should be contacted to collect adverse events that occur within 30 days after the last dose of the last study treatment. Additional information on reporting adverse events may be found in Section 12.

If the subject requires subsequent antilymphoma therapy in the interim period following the last dose of study treatment and the End-of-Treatment visit, then this visit should be completed earlier, ie, just prior to initiation of subsequent antilymphoma therapy. Refer to the Time and Events Schedule for a complete list of procedures to be performed ([Table 1](#), [Table 2](#), [Table 3](#), and [Table 4](#)).

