At the time of PD or if residual disease is present upon completion of 3 cycles, the subject is considered eligible to receive subsequent antilymphoma therapy. Subsequent antilymphoma therapy will be recorded in the electronic CRF. Subjects with residual disease who receive subsequent antilymphoma therapy will be followed until PD, end of the study, or death. Investigators should maintain adequate contact with the subject to obtain follow-up information on safety and survival status. Where allowed by local law, public records may be used to document death. Any new malignancy reported during the posttreatment follow-up phase will be recorded in the CRF (Section 12.3.4).

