9.2.5.2. Response Categories

Assessment of tumor response and progression will be according to the International Pediatric NHL Response Criteria ([Table 9](#) and [Table 10](#)).³⁶ Disease response will be evaluated by radiological imaging, physical examination, or other procedures as necessary, including but not limited to review of hematology, clinical chemistry, and lumbar puncture results. Disease evaluations, for the purpose of the study result analyses, will be reviewed by an IRC blinded to study treatment information and independent of investigators and personnel who are involved in conduct of the study. As part of the central review, radiographic evaluations will be assessed by an independent radiologist and relevant clinical data will be assessed by an independent oncologist. Detailed procedures will be described in a separate charter.

Table 9: International Pediatric NHL Response Criteria

Criterion	Definition
CR	Disappearance of all disease (3 designations)
CR	CT or MRI reveals no residual disease or new lesions Resected residual mass that is pathologically (morphologically) negative for disease (detection of disease with more sensitive techniques described as supporting data [Table 10]) BM and CSF morphologically free of disease (detection of disease with more sensitive techniques described as supporting data [Table 10]) with no new lesions by imaging examination
CR _b	Residual mass has no morphologic evidence of disease from limited or core biopsy (detection of disease with more sensitive techniques described as supporting data), with no new lesions by imaging examination BM and CSF morphologically free of disease (detection of disease with more sensitive techniques described as supporting data [Table 10]) No new or PD elsewhere
CR _u	Residual mass is negative by FDG-PET; no new lesions by imaging examination BM and CSF morphologically free of disease (detection of disease with more sensitive techniques described as supporting data [Table 10]) No new or PD elsewhere
PR	50% decrease in SPD on CT or MRI; FDG-PET may be positive (Deauville score of 4 or 5 with reduced lesional uptake compared with baseline); no new or PD; morphologic evidence of disease may be present in BM or CSF if present at diagnosis (detection of disease with more sensitive techniques described as supporting data [Table 10]); however, there should be 50% reduction in percentage of lymphoma cells

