2.7. Imputation Rules for Missing AE Date/Time of Onset/Resolution

In general, imputation of missing dates will be made for AE onset date, AE resolution date, date of death, start and end dates of prior, concomitant and subsequent therapies, and date of initial diagnosis according to the following rules. Start date will be imputed before end date.

- If date is completely missing, no imputation will be made.
- If year is missing, no imputation will be made.
- If only year is present but month and day are missing, then June 30th will be used.
- If only day is missing but year and month are available, then the 15th of the month will be used.

However, the above imputations will be modified by the following rules:

- For initial diagnosis if such imputed date is on or after the randomization date, then randomization date - 1 will be used.
- If such imputed date for prior therapies or initial diagnosis is on or after the randomization date, then randomization date - 1 will be used. If such imputed date for subsequent therapies is before date of last dose, then date of last dose +1 will be used.
- The imputed start date for subsequent therapies will be adjusted sequentially using the following steps:
 - If the imputed start date is before the treatment discontinuation date or last dose date if no treatment discontinuation date but in the same year and month, then the treatment discontinuation date or last dose date if no treatment discontinuation date will be used.
 - If subsequent therapy end date is not missing and is before the imputed subsequent therapy start date, then the subsequent therapy end date will be used as the start date.
- If the imputed date is for a date of death and is before the last date that the subject is known to be alive, the latter date will be used.
- The imputed AE start date will be adjusted sequentially using the following steps:
 - If the imputed date is in the same year and month as but day before the first dose date, then the first dose date will be used, or if it is in the same year and month as but day after the last dose date + 30 days, then the last dose date + 30 days will be used.

- If AE end date is not missing and the imputed AE start date is after the AE end date, then the AE end date will be used.
 - If the imputed AE start date and is after date of death, then date of death will be used

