Overall Response Rate in Part 2	Primary	IRC assessed ORR chi-square test, Logistic regression model	ITT subjects with measurable disease at baseline
	Sensitivity	Investigator assessed ORR chi-square test, Logistic regression model	
	Subgroup	Logistic regression model	
Tumor Volume Reduction Rate		Analysis of variance (t-test) for percent decrease in the sum of the products of the lesion diameters at Day 14	ITT subjects with measurable disease at baseline
Time to Response		Non-stratified log-rank test, as the time interval from randomization to response for those subjects who respond as	ITT subjects who responded

Table 3: Summary of Efficacy Analyses to be Performed

Endpoint	Analysis	Analysis Method	Population
		assessed by IRC.	
Duration of Response		Non-stratified log-rank test, as the time interval from date of initial documentation of a response to the date of first documented evidence of progressive disease (PD) or death as assessed by IRC.	ITT subjects who responded
Rate of Subjects Who Proceed to Stem Cell Transplantation		Chi-square test for percent of subjects who proceed to stem cell transportation, Logistic regression model.	ITT
Other			
Subsequent Therapy		Descriptive summary Non-stratified log-rank test for the effect of subsequent antilymphoma therapy or a conditioning regimen for stem cell transplantation on overall survival, will be performed, as appropriate.	ITT subjects
Risk factors		Non-stratified Cox proportional hazards model using covariates to analyze the effect on EFS and survival will be performed, as appropriate.	ITT

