5.5. Secondary Endpoints

5.5.1. Overall Survival

Overall survival is defined as the duration from the date of enrollment (in Part 1) or randomization (in Part 2) to the date of the subject's death. Overall survival will be analyzed using the non-stratified log-rank test for treatment comparison in Part 2. Survival time of living subjects will be censored on the last date a subject is known to be alive or lost to follow-up.

The overall survival distribution and median overall survival with its 90% confidence interval will be estimated using the Kaplan-Meier product-limit method. The hazard ratio for ibrutinib+CIT relative to CIT alone and its associated 90% confidence interval will be calculated based on the non-stratified Cox proportional hazards model.

The same subgroup analysis used for EFS will be performed for OS if the number of events within each subgroup is sufficient.

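### The exploratory log-rank test of later therapy on overall survival (SAP 5.5.7) defines neither groups nor time origin; read as ever versus never treated, it is biased in a direction the documents do not fix

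*SAP*

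**What the plan says.** SAP 5.5.7 lists among its exploratory analyses: "Non-stratified log-rank test for the effect of subsequent antilymphoma therapy or a conditioning regimen for stem cell transplantation on overall survival". The Subsequent Therapy row of SAP Table 3 repeats it: "effect of subsequent antilymphoma therapy or a conditioning regimen for stem cell transplantation on overall survival, will be performed, as appropriate". Neither gives comparison groups, a landmark or any handling of when therapy starts. Protocol 11.3.2 foresees an exploratory look at subsequent therapy and OS but names no method. The time origin is in SAP 5.5.1: "Overall survival is defined as the duration from the date of enrollment (in Part 1) or randomization (in Part 2", the clock stopping at death.

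The protocol describes three routes to later therapy:
- **Transplant in remission** (Protocol 9.1.3): "If CR is confirmed at the end of 2 cycles of treatment, then the subject is eligible to proceed to stem cell transplantation".
- **Therapy after PD**, and **therapy for residual disease** (Protocol 9.1.4): "At the time of PD or if residual disease is present upon completion of 3 cycles, the subject is considered eligible" for further treatment. Protocol 8.4 sets the same two conditions.
- Protocol 8.4 confirms that treatment without PD is foreseen: "Subjects who have not progressed while on therapy and who receive subsequent therapy for NHL will continue to be followed until PD".

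Three neighbouring items do not fill the gap. The first bullet of SAP 5.5.7 allows a Cox model with unspecified covariates. SAP 5.5.2 censors OS at later therapy. The third bullet of 5.5.7 gives counts by therapy type and a listing.

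**The concern.** A log-rank test compares groups whose membership is known at time zero. Here membership is decided by what happens after randomization. A subject who dies early is counted as never treated, and a treated subject cannot have died before treatment. That is immortal time, and it favours therapy. Transplant in remission adds selection of good-prognosis subjects in the same direction. Therapy given because of PD or residual disease selects subjects in a worse state, which works the other way. One test, as worded, appears to pool all three.

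At stake is a reported effect of transplant or salvage therapy, in a rare pediatric disease, that reflects who was treated and when.

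**Working it through.** **1. The plan's own figures.** The documents give no power or expected result for this test. The nearest figure is the EFS power in SAP 1.4: √(60 × 2/3 × 1/3) × ln 2 − 1.645 = 3.651 × 0.693 − 1.645 = 0.886, giving 81.2% against the stated 80% or more. It reproduces, but says nothing about this analysis.

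**2. Where the bias enters.** The log-rank numerator is U = Σ(d₁ − d·n₁/n) over death times. Ever-treated subjects contribute to n₁ before treatment, when d₁ is zero for them by construction. Every earlier death therefore moves U towards benefit. With 28-day cycles, transplant after two cycles cannot start before 56/30.4 = 1.8 months, nor therapy for residual disease before 84/30.4 = 2.8 months (1.4 and 2.1 months with 21-day cycles). In the other direction, suppose survival after PD has median 4 months and death without PD runs at 1% per month (both assumed). The hazard then rises from 0.01 to ln 2/4 = 0.173 per month at PD, about 17-fold, just before salvage begins.

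**3. Size under no true effect.** Route shares, uptake and delays are not in the documents, so two sets of assumptions were simulated, each with a true therapy hazard ratio (HR) of 1, 72 subjects and 5% nominal error per side.
- *Set A:* median time to PD 5 months (the protocol's control-arm median EFS, borrowed); 0–20% long-term non-progressors; post-PD median 4 months (2.5–6 in the post-PD-only runs); non-PD death 1% per month (0.5% and 2% also run in one mix); residual disease in 40% of non-cured subjects PD-free at month 3, doubling later PD hazard; uptake 75% for a single route.
- *Set B:* remission 45%, residual disease 25%, early PD 30%; base uptake 50%, 60% and 60%, varied from 0 to 90%; post-PD median 2.5 months, approximated from the figure in Protocol 1.2, which runs from study entry.

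Ever versus never from randomization, with false benefit / false harm in brackets where reported:

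| Routes used | Set A HR | Set B median HR |
|---|---|---|
| Remission transplant only | 0.31–0.44 (82–98% / not stated) | 0.19 (100% / 0%) |
| Post-PD therapy only | 0.86–2.09 (0–13% / 2–85%) | 1.77 (0% / 65%) |
| Residual disease only | 0.81–1.20 (0–10% / 1–8%) | 1.37 (0% / 20%) |
| Mixed | 0.47–1.45 (0–83% / 0–34%) | 0.29 mostly transplant (100% / 0%); 0.81 base (20% / 1%); 1.61 mostly post-PD (0% / 51%) |

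At set A's main settings, transplant only gives 0.37 and post-PD only 1.46: the 0.4 and 1.5 quoted as illustrations. Even one route has no fixed sign. Set B with a poorer population and slower post-PD therapy gives 0.84. In smaller trials the mixed range is 0.46–1.42 (set A, N=48) and 0.28–1.57 (set B, N=46). With a true HR of 0.6 and mostly post-PD therapy, the ever/never comparison shows 1.32.

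**4. Which time-dependent model removes it.** Set B, ten null scenarios, median HR for a single later-therapy term:

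| Time-dependent terms | Range (truth 1) |
|---|---|
| Therapy only | 0.21–7.13 |
| Therapy and PD | 0.61–1.65 |
| Therapy, with PD and residual disease merged | 0.54–1.77 |
| Therapy, PD and residual disease, separate | 0.96–1.02 |

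With separate terms, the true HR of 0.6 in step 3 is recovered as 0.60. In set A, splitting therapy into conditioning and subsequent therapy gives 0.94–1.03 and 0.96–1.04 at N=72.

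**5. What remains.** At N=48 that split model gives null HRs of 0.86–1.02 and 0.91–1.08, with false harm up to 10.5%. If fitter subjects are treated more often, a null therapy still shows 0.66–0.77 (set A) or 0.66–0.80 (set B). In set B's base mix the standard error of log HR is 0.33 at N=72 and 0.42 at N=46. The 90% limits are then the estimate divided and multiplied by exp(1.645 × 0.33) = 1.7 or exp(1.645 × 0.42) = 2.0.

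**The case against.** **The SAP never says ever versus never.** True. A reader might infer that a biased analysis is already fixed in the plan; the documents do not support that. The wording could also mean two comparisons, one for subsequent therapy and one for conditioning. So the bias is conditional on the natural reading. But a landmark or other timing rule would have to be written, and none is.

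**The numbers are the analyst's own.** Also true. Set B falls outside several of set A's ranges, so neither set bounds the bias in this trial. Protocol 1.1 and 1.2 give some outside figures, including 6 subjects in a study with 20 evaluable proceeding to high-dose therapy, but not the mix of routes here. What survives is that the sign changes within plausible inputs. A reader might infer that the test must exaggerate benefit, because immortal time usually does. The PD and residual-disease routes show that this does not follow.

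**The replacement model is fragile.** This stands. Enrolment stopped after the futility boundary was reached at 31 EFS events. The final number is not given; the plan expected 46 subjects at the interim. In set A at N=48 (30–41 deaths), the ratio of upper to lower 90% limit for transplant was 5.4–14.4. This argues for description as the default, not for keeping the log-rank test.

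**It is exploratory and to be done only as appropriate.** This limits the consequence, but that phrase supplies no method, and the log-rank test is the one named.

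**Conclusion.** The concern holds conditionally. If the groups are ever and never treated from randomization, the named test is invalid for its stated purpose, and with an ineffective therapy it can show apparent benefit or apparent harm. The illustrative HRs show scale only and are not predictions for this trial. The conclusion rests on the ever/never reading, on therapy starting after randomization by routes of differing prognosis, and on assumed shares and delays.

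A stronger reading, that this undermines the trial's conclusions, is not supported. The analysis is outside the ordered list in SAP 5.2 and does not touch the EFS test, alpha, sample size or secondary hierarchy. Severity: could be improved.

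**What to change.** In SAP 5.5.7 and the Subsequent Therapy row of Table 3, remove the log-rank test. By default, report later therapy descriptively by type and by route (remission transplant, after PD, residual disease), extending the counts and listing already planned.

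If an association with OS is estimated, specify before database lock:
- **Model.** Cox regression from randomization with treatment arm, time-dependent indicators for transplant conditioning and for subsequent therapy, and separate time-dependent terms for PD and for residual disease after Cycle 3.
- **Residual disease.** Define it and say whether an IRC partial response counts. Protocol Table 9 allows that in a partial response "morphologic evidence of disease may be present in BM or CSF if present at diagnosis".
- **Date order.** SAP 2.7 says "The imputed start date for subsequent therapies will be adjusted sequentially using the following steps", but those steps refer to treatment discontinuation, last dose and therapy end, never to PD. Add a rule for when an imputed therapy date and PD fall close together.
- **Minimum numbers.** Fit only with enough recipients and deaths; otherwise stay descriptive. As a guide, in set A's mixed runs at N=48, 2–4 transplant recipients gave a median 90% limit ratio of 16.6 and 9% of fits were not estimable, against a ratio of about 6 with 10 or more. The cut-off is a choice.
- **Label.** A non-causal association.

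The cost is SAP wording and modest programming. Protocol 8.4 already collects start dates of subsequent therapy, and SAP 5.4.3 and 5.5.2 already need the timing of therapy and conditioning. PD ascertainment is less complete late on, because scheduled efficacy assessments end at PD, the clinical cutoff or 3 years (Protocol 9.1.4). The downsides are wide intervals and remaining confounding by fitness.

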6. SAFETY

Safety will be analyzed using the incidence and severity of AEs, laboratory tests, and electrocardiogram (ECG) measurements. Unless specified otherwise, all safety analyses will be based on the safety analysis set. Descriptive statistics will be reported for all safety data. Inferential statistics are not planned to be performed on safety data.

The baseline value for safety analysis is defined as the value collected at the time closest to and prior to the start of study medication.

Unless otherwise stated, safety data will be summarized by treatment arm as treated.

6.1. Adverse Events

Table 4 provides a summary of adverse events analyses to be performed.

Table 4: Summary of Adverse Event Analyses to be Performed

Category	Analysis	Sorted By	Cut off	Drug-Related TEAE
General	Overall summary			✓
	TEAEs	SOC+ PT+ toxicity grade; PT+ toxicity grade	10%, 5%	✓
	Serious TEAEs	SOC+ PT + toxicity grade; PT+ toxicity grade	2%	✓
	Grade 3 or worse TEAE	PT+ toxicity grade	2%	✓
	TEAEs leading to treatment discontinuation (ibrutinib+CIT/CIT)	PT + toxicity grade		✓
	TEAEs leading to death	PT + toxicity grade		
	TEAEs leading to dose modification or modification (ibrutinib+CIT/CIT)	PT + toxicity grade		
	AEs of clinical interest (Hemorrhagic events)	PT + toxicity grade		
	Other safety observations (eg, other malignancies, eye disorder)	PT + toxicity grade		
	Deaths within 30 days of last dose	Reason for death		
Subgroup	Overall summary			
	TEAEs	SOC+ PT+ toxicity grade		
Exposure adjusted incidence rate	Overall summary			
	TEAEs	SOC+ PT+ toxicity grade; PT+ toxicity grade	1 per 100 patient month	
	Serious TEAEs	SOC+ PT + toxicity grade; PT+ toxicity grade	0.1 per 100 patient month	

